9.2. Definition of a Serious Adverse Event

A serious adverse event (SAE) is defined as any AE related to study specimen collection that **meet one / more of the seriousness criteria below:**

- Death
- Life-threatening (places the subject at immediate risk of death from the event as it occurred);
- **Requires** in inpatient hospitalization (**unplanned hospitalization**) or prolongation of existing hospitalization;
- Persistent or significant **disability** / incapacity;
- Congenital anomaly/birth defect **or fetal/neonatal death**; or
- **Important Medical Event:** Based on appropriate medical judgment, may jeopardize the subject's health and may require medical or surgical intervention to prevent one of the other outcomes listed in this definition.

9.3. Definition of Reportable Event

A Reportable Event (RE) is defined as any event outside of an AE definition that meet one / more seriousness criteria as stated in the section 9.2.

9.4. Definition of an Unanticipated Problem

An unanticipated problem is defined as any incident, experience, or outcome that is defined as:

1. Unexpected in terms of nature, severity, or frequency in relation to:
 - the research risks that are described in the research protocol and informed consent document or other study documents; and
 - the characteristics of the subject population being studied; and
2. Related or possibly related to the participation in the research; and
3. Places subjects or others at a greater risk of harm (including physical, psychological, economic, or social harm) than was previously known or recognized or is an SAE.

10. ETHICAL CONSIDERATION

10.1. Informed consent process

Informed consent is a process in which information is presented to enable persons to voluntarily decide whether or not to participate as a research subject. It is an ongoing conversation between the human research subject and the researchers covering the essential

information about the study which begins before consent is given and continues until the end of the subject's involvement in the research.

Their parents or legal guardians will sign an ICF after discussion of essential information about the research by the study staff. This will include the purpose of the study, duration, procedures, alternatives, risks, and benefits. Subjects and/or their parents or legal guardians will have the opportunity to ask questions about the study and have their questions answered.

Legal guardian is a person who has rights and responsibilities to look after / take care the child. They are usually related by blood, members of the family, or legal parents of an adopted child. Neighbor, friends, or maid of the family cannot serve as the child's legal guardian.

Subject's parent or legal guardian will sign/thumb print an appropriate informed consent document prior to any procedures being done specifically for the study. The subjects may withdraw consent at any time throughout the course of the trial. A copy of the informed consent document will be given to the subjects for their records. The researcher will document the signing of the consent form in each subject's study record.

10.2. Illiterate Subject's parent or legal guardian

If the subject's parent or legal guardian is illiterate, oral consent will be obtained. The administrator of the oral consent will sign and date the form. The subject's parent or legal guardian will thumbprint the consent form. An impartial witness should be present during the entire informed consent discussion and should sign and date the consent form.

10.3 Parental Consent

Parental/legal guardian consent will be obtained for all study subjects. For further information, please refer to IRB checklist: studies involving children.

10.4. IRB Review

Prior to the implementation of the protocol, the protocol and ICF for this study will be submitted for approval to the appropriate IRB. Any change to the protocol, ICF, or a change of the site investigator, will only be made after approval from the IRB. Records of the IRB review and approval of all the documents pertaining to the study will be kept on file by the site investigator and are subject to inspection at any time during the study. Continuing

reviews or study progress report will be submitted according to the requirement of the appropriate IRB, but once a year at a minimum.

10.5. Participant Confidentiality

All records will be kept *confidential* to the extent provided by the law. The study monitors and other authorized representatives may inspect all documents and records required to be maintained by the site investigator, including, but not limited to, medical records. Records will be kept in a locked cabinet, and all computer entry and networking programs will be done with coded numbers only. Clinical information, attributable to the subject, will not be released without written permission of the subject, except as necessary for monitoring by INA-RESPOND and the EC/IRB.

10.6. Rationale for Subject Selection

Children under age 2 month are excluded from participating in the study due to concerns regarding blood volume.

10.7. Benefits

This study is meant as a pilot study to provide knowledge on the etiology of pneumonia among hospitalized pediatric patients in study hospitals and to identify areas of potential research in the future. It may not provide direct benefit to participants. All test may help the physician to establish diagnose.

The study will provide two blood cultures, sputum culture, CBC, CRP, Procalcitonin and rapid diagnostic test for Influenza, RSV, and Legionella as listed in section 4.6.6 and 4.6.7. Transportation costs and time compensation will be reimbursable up to Rp.150,000 for study Visit Day 14th after hospitalization. The study will not provide costs for routine care or hospitalization.

10.8. Risks and Discomforts

This is a minimal-risk, observational study and does not involve experimental interventions. The only study intervention is a blood draw and all other procedures are considered as part of standard care for hospitalized pneumonia patients.

The hazards of blood drawing are minimal and consist of mild discomfort and or bleeding at the venipuncture site, bruising and rarely fainting and local infection. In case of any immediate serious side effect like fainting the patient will be stabilized by the study team if needed.

The hazards of sputum collection are minimal and consist of mild discomfort when subjects tried to produce sputum to be collected.

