- Comply with all study procedures including to store required specimens for diagnostic testing and archiving.

Exclusion criteria

- Being Hospitalized for more than 24 hours at enrollment
- Having a cancer or history of cancer
- Having a history of long term exposed of steroid (at the minimum of 2 months)
- Having any condition that might interfere with study procedure and compliance (based on clinicians' judgement)

Study Procedures
Participants who meet the inclusion and exclusion criteria will be enrolled and then having a daily follow up for maximum of 13 days' hospitalization. Next follow up will be taken time at day 14 th after hospitalization date, either on ward or polyclinic. The participations will be ended by day 30 th after hospitalization date when the called follow up is done by the Research Assistant (RA).
This study will collect demographic data, medical history, clinical data, treatment, and risk factors of pneumonia. The study also recorded the supporting examination results include but not limited to Complete Blood Count (CBC) results, blood gas analyses result, CRP, PCT, culture result, rapid test for influenza, Respiratory Syncytial Virus (RSV), legionella, and chest X-ray. In order to produce a robust data, this study will conduct the serological and molecular tests at the reference laboratory.
Whole blood, serum, urine, Nasal Pharyngeal Swab (NPS), sputum/induced sputum, and other respiratory specimens (if available) will be collected for storage and testing at enrollment. Any left-over respiratory specimens and/ or plasma on day 2 and 3 of hospitalization will also be collected to be stored. For additional, at day 14 th after hospitalization serum will be processed from 4 mL of blood for archiving and testing at the reference laboratory.

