4.3. Type and Design of Study

This study is an observational study, conducted at the pediatric department at three hospitals in Indonesia. It will recruit hospitalized children aged between 2 months to 5 years who meet the inclusion and exclusion criteria. Participants will be followed up for maximum 13 days' hospitalization. At day 14th after hospitalization date each participant will be assessed for his/her symptoms, clinical data, clinical outcome, and serum specimen collection. The end of their participation will be ended on day 30th after hospitalization date, after followed up phone from RA.

Laboratory test procedures will be conducted during the study and/or after study completion. Chest X-Ray, CBC, blood and respiratory specimen cultures including antibiotic resistance test will be performed either as part of standard of care or study addition. Rapid tests for Influenza A and B; Respiratory Syncytial Virus (RSV); and Legionella will be performed as study requirement. C-reactive protein (CRP) and Procalcitonin (PCT) will also be measured for study interest. Molecular assays to identify bacterial and viral pathogens and serological assays to detect infections of several viruses and bacteria will be conducted at the reference laboratory. Any left-over respiratory specimens and/or plasma from day 2 and 3 hospitalization will be stored for archiving.

Specimen that will be stored for archiving, will be maintained for further laboratory testing for up to 5 years after the study is completed. After 5 years, with the decision of Steering

Committee and Governing Board, specimens in the INA-RESPOND specimen repository in NIH RD Jakarta, will either be destroyed, or after IRB approval, transferred to another existing protocol or a repository.

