3.6.7. Laboratory procedures for Molecular and Serological Testing

This study will carry out molecular and serological testing that will be done at the reference laboratory. The study will cover all the costs of those tests.

Table 1 and Table 2 will furtherly explain the required specimen volume and tests needed. Also see appendix A for the work flow.

Table 1. The research specimen and laboratory testing

Visit /Time	Collected Specimen	Amount	Laboratory Testing at	
			Hospital	Reference Lab
Enrollment (up to 24 hours after enrollment)	Whole Blood	2 x 1 ml – 2 ml blood 1 x 3 ml blood	Blood culture (2 sides) CBC	PCR (Streptococcus pneumonia, Staphylococcus aureus, Haemophilus influenza)
	Serum	1 x 4 ml blood	CRP, Procalcitonin, HIV (can be done up to 5 days after enrollment)	Serology IgM and IgG (Influenza A, B, RSV, Parainfluenza virus, Adenovirus, Mycoplasma pneumonia, Chlamydia pneumonia, Bordetella pertussis, Legionella pneumonia)
Enrollment (up to 48 hours after enrollment)	Urine	1 ml – 3 ml urine	Rapid test Legionella antigen	PCR (Legionella pneumoniae, Leptospira)
	Nasopharyngeal swab	2 VTM (1.5 ml)	Rapid test Influenza Rapid test RSV	PCR (18- Viral Panel)
	Sputum/induced sputum	2 ml	Culture, MTB (genexpert, if AFB positive)	PCR (11 Bacterial and 18 viral panel)
	Other resp specimen (leftover – effusi pleura, BAL)	If available	Culture, MTB (genexpert, if AFB positive)	PCR (11 Bacterial and 18 viral panel)
Daily study visit during hospitalization	Left-over respiratory specimen and/or plasma (Daily study visit day 1 & 2 (day 2 & 3 of hospitalization)	If available	None	TBD
Study Visit Day 14th after hospitalization	Serum	4 ml blood	None	Serology IgM and IgG (Influenza A, B, RSV, Parainfluenza virus, Adenovirus, Mycoplasma pneumonia, Chlamydia pneumonia, Bordetella pertussis, Legionella pneumonia)
Follow-up Day 30 th after hospitalization	None	None	None	None

NOTE: Maximum amount of blood drawn in pediatric patients weight 7.3 – 45.5 kgs is 10 ml - 30 ml at any one time or 60 ml – 350 ml cumulative during hospitalization or maximum 1 month (Garza D, Becan-McBride K).

Table 2. PCR Panel for Bacterial & Viral Pathogens

PCR Viral Panel	PCR Bacterial Panel
Human Influenza A virus	Haemophilus influenza
Human Influenza B virus	Streptococcus pneumoniae
Adenovirus	Legionella pneumoniae
Enterovirus	Mycoplasma pneumoniae
Respiratory Syncytial Virus A	Chlamydia pneumoniae

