9.1. Definition of an Adverse Event

An adverse event (AE) is any untoward or unfavorable medical occurrence in a human subject that occurs within 48 hours of a study-related study blood specimen collection that is possibly, probably, or definitely related to the study specimen collection. Any event outside of this 48 hours' window period will not be considered an AE for this study.

But for induce sputum collection, if the subject's conditions worsening from the original condition prior to the enrollment is observed such as, but not limited to, increase in coughing or wheezing, it will be considered as AE for this study if occurred within 2 hours after sputum induction procedure. For every AE that occurs based on the subject's conditions, the RA needs to consult with the site PI or site Co-PI to determine AE or not.

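### Section 10.8 treats everything except the blood draw as standard care, which other sections contradict, and similar blood-only wording leaves gaps in the adverse-event definition and the summary report

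*Combined protocol and SAP*

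**What the plan says.** Section 10.8 describes the study as minimal-risk and states: "The only study intervention is a blood draw and all other procedures are considered as part of standard care for hospitalized pneumonia patients". It lists hazards for blood drawing. For sputum it gives only "mild discomfort when subjects tried to produce sputum to be collected". It does not mention induction, and it states no hazard for the swab or for urine.

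Other sections describe these procedures differently:

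- Section 4.3: "Rapid tests for Influenza A and B; Respiratory Syncytial Virus (RSV); and Legionella will be performed as study requirement". The same section says cultures may be either standard care or a study addition.
- Research Summary, Study Procedures: "serum, urine, Nasal Pharyngeal Swab (NPS), sputum/induced sputum, and other respiratory specimens (if available) will be collected for storage and testing at enrollment".
- Table 1, in the section printed as 3.6.7, is titled "The research specimen and laboratory testing". It schedules urine, swab and sputum/induced sputum for every child at enrolment, with PCR at the reference laboratory.
- Section 10.7: the study provides the sputum culture and the three rapid tests, and does not pay for routine care.

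On safety, section 9.1 defines an AE by a 48-hour window after study blood collection. It then adds a separate rule for induced sputum, covering worsening of the child's condition such as "increase in coughing or wheezing, it will be considered as AE for this study if occurred within 2 hours after sputum induction procedure". Section 9 uses two scopes: any study specimen collection for serious events, and the research blood draw for the summary sent to the IRB at continuing review.

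**The concern.** The protocol gives two incompatible answers to a basic question: which procedures are done because the child is in the study? That answer determines what counts as a research risk and what has to be reported.

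Two things are at stake. First, the protocol's risk text is incomplete in the section that asserts minimal risk. It describes a child trying to produce sputum, although eligibility starts at 2 months of age and the specimen list includes induction. Second, a similar blood-only scope appears in two operative safety clauses, the general AE definition and the summary report. If the plan is followed as written, some non-serious events from study-required collections will be neither classified nor summarised as study AEs. The IRB's periodic picture of collection-related harm would then be that of the blood draws.

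**Working it through.** No arithmetic applies, and the plan gives no figure to reproduce. The check sets the sections side by side for the four specimen types that Table 1 schedules for every child at enrolment.

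| Collection | Status in 10.8 | Status elsewhere | Hazard in 10.8 | Non-serious event an AE under 9.1? | In the section 9 summary? |
|---|---|---|---|---|---|
| Blood | Study | Study (Table 1) | Stated | Yes, within 48 hours | Yes |
| Urine | Standard care | Rapid test required by the study (4.3); research specimen (Table 1) | None | No route of its own | No |
| Nasopharyngeal swab | Standard care | Rapid tests required by the study (4.3); research specimen (Table 1) | None | No route of its own | No |
| Sputum/induced sputum | Standard care | Research specimen (Table 1); culture is standard care or study addition (4.3) and provided by the study (10.7) | Mild discomfort only | Yes, for worsening within 2 hours of induction | No |

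**Status.** Section 10.8 recognises 1 of the 4 as a study procedure. For swab and urine the contradiction is direct, because the rapid tests run on them are a study requirement. For sputum the status is mixed, but mixed status still conflicts with a sentence that puts all other procedures under standard care.

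**Hazards.** Section 9.1 names increased coughing or wheezing, and it names them for induction only. Section 10.8 carries neither over.

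**AE definition.** The general clause in 9.1 sets its window by blood collection, then asks whether the event is related to the study specimen collection. Read strictly, the specimen is the blood. Read generously, a swab or urine event could count, but only if it happened to fall within 48 hours of a blood draw. On neither reading does swab or urine collection have a window of its own.

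**Summary report.** Here both the window and the relatedness test refer to the research blood draw, so even the generous reading of 9.1 does not help. An induction event that 9.1 makes an AE, if not serious, is left out.

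**Serious events.** Section 9 applies the wider scope of study specimen collection. Section 9.3 makes any serious event outside the AE definition a Reportable Event, which goes to the IRB within 10 working days or per local requirement. Such events are not lost. One difference remains: site PI evaluation within 24 hours is stated for SAEs and not for Reportable Events.

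**The case against.** The strongest reply is that 10.8 is descriptive text and does not modify the safety rules. Section 6.3 defines study specimens as specimens collected from study subjects, with no exemption for standard-care collection. Section 9.1 states that worsening within 2 hours of induction is an AE for this study. Section 9.3 backs this up for serious events. This stands, and it rules out several stronger conclusions that a reader might draw.

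- **That AE attribution is wrong throughout, or that sites may dismiss deterioration after induction as standard care.** Section 9.1 attributes it to the study expressly. Consultation with the site PI or Co-PI leaves room for judgement, but the rule itself is clear.
- **That wheeze after induction is unexpected under 10.8 and expected under 9.1, so sites would report it differently.** Section 9.4 judges against "the research risks that are described in the research protocol and informed consent document or other study documents". Section 9.1 is part of the protocol and names the wheeze, and 9.4 has further conditions.
- **That parents are not told of the risk, or that the IRB was misled.** The consent pages were removed from the text available for review, and the IRB reviews the consent form as well as the protocol. Only the protocol's own risk wording can be criticised.
- **That swab and urine carry the named respiratory risk.** Section 9.1 attaches it to induction alone.

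The reply does not reach the two blood-only phrases. The definition in 6.3 does not alter the blood-anchored window in 9.1 or the blood-draw limit on the summary report. An amendment confined to 10.8 would leave both in place.

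**Conclusion.** The point holds in a limited form. The 10.8 sentence is contradicted by 4.3, the Research Summary, Table 1 and 10.7. Its sputum hazard is narrower than 9.1, and the swab has none. The AE scope is inconsistent: non-serious swab or urine events have no AE route of their own, and non-serious induction AEs are omitted from the summary report.

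The size in events is unknown, since the documents give no event rates. The planned 275 participants are only a ceiling: induction is an alternative to ordinary sputum collection, some collection may be standard care, and the number of study-driven inductions is not stated. The count of 1 in 4 describes how complete the text is and does not measure risk, because urine collection is not comparable to induction.

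The conclusion assumes that sites apply sections 9 and 9.1 as worded and that the Manual of Procedures, which is not available here, does not widen the scope. A non-serious event that met all the conditions of 9.4 would still be reported as an unanticipated problem.

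**What to change.** 1. In 10.8, replace the sentence on the only study intervention with a list of the study-required collections: enrolment and day-14 blood, nasopharyngeal swab, urine, and sputum or induced sputum where it is not done as standard care. Carry over the induction risk already named in 9.1 and state a risk for the swab.
2. Use one scope, study specimen collection, in 9, 9.1 and 9.2. This means replacing the blood-only wording in the general AE definition of 9.1 and in the summary-report paragraph of section 9. Keep the existing induction rule and say how it sits beside the general window.
3. Check that the consent form carries the same list of procedures and risks.

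The cost is a wording amendment submitted to the IRB, a check of the consent form, and possibly a few more reported AEs. No procedure, visit or staff is added.

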10.9. Plan for Maintaining Privacy and Confidentiality of Subject Records

The information obtained during the conduct of this clinical study is confidential. The results of the research study may be published according to the INA-RESPOND policy, but subject names or identities will not be revealed. To maintain confidentiality, study documents, including case report forms will be kept in locked filing cabinets, in a secure room at each clinical research site.

10.10 Recording/Documentation

At each contact with the subject, assessment information will be elicited by appropriate questioning and examination, and they will be recorded on source documents. Source documents may include worksheets, progress notes, laboratory reports, consult notes, and data collection tools. Data is to be transcribed onto CRFs from source documents on an ongoing basis during the study. The study monitor may review and audit all documents and records required to be maintained by the site investigator.

Any type of corrections to study documents should be initialed and dated by the person who is making the correction. The site investigator is responsible for ensuring that the data collected are complete, accurate, and recorded in a timely manner. All CRFs should be reviewed by the site investigator and signed as required with written signature. CRFs will be maintained and kept in locked cabinets at the site for at least 5 years after study completion.

Each subject's name will be paired with a numeric code in the enrollment log. Access to data identifying subjects will be kept in a locked file, accessible only by study staff. Finally, the importance of subject confidentiality will be impressed upon all research staff. The site investigator is responsible for the accuracy and completeness of the data reported.

11. PROTECTION OF INTELLECTUAL PROPERTY (IPR), MATERIAL TRANSFER AGREEMENT (MTA), AND GENETIC RESOURCES AND TRADITIONAL KNOWLEDGE (GRTK)

